6.13.4.4 Autism Behavior Inventory - Clinician (ABI-C)

The ABI-C is a 14-item rating scale to assess the core features of Autism Spectrum Disorder (ASD) as well as common associated behaviors. When completing the ABI-C, the clinician is asked to rate the overall severity/level of impairment of each item over the past week on a 7-point Likert type scale. In general, the ratings correspond

to the following: 1. None, No symptoms present to 7. Very Severe, Persistent interference with function or adaptation.

The clinician will rate the subject based on both behavioral observation and clinician interview. The ABI-C will be administered at Visits and and may be assessed via telehealth if required due to a COVID-19 related reason.

The ABI-C total score will be derived at each visit as the total score based on the 14 items, with a higher score indicating worse ASD severity. If one or more of the 14 items is missing then the total score will be set to missing. If a subject's in-clinic visit is unavailable, the data will be imputed with the corresponding telehealth assessment.

The ABI-C core autism symptoms subscore will be derived at each visit as the total score based on the first 8 items, with a higher score indicating worse ASD severity. If one or more of the 8 items is missing then the total score will be set to missing. If a subject's in-clinic visit is unavailable, the data will be imputed with the corresponding telehealth assessment if available.

A MMRM will be fitted to the change from baseline over time in the ABI-C total score and the ABI-C core autism symptoms subscore in a similar manner to the primary estimand (see Section 6.13.1.1). The model will include the baseline value as a covariate, treatment group, age group and visit as fixed effects, and the treatment-by-visit interaction.

Summary statistics of observed values with corresponding change from baseline will be presented as continuous by visit and treatment. Line plots will present the adjusted LS mean changes from baseline to end of treatment and SEs, as estimated by the MMRM model, by treatment group.

The ABI-C data will be listed.

6.13.4.5 Vineland Adaptive Behavior Scale

| The Vineland Adaptive Behavior Scales - | - (Vineland measures |
|--|---|
| personal and social skills needed for everyo | day living. The scales are organized into a |
| | . A subject's |
| overall level of adaptive functioning is descr | ribed by the Adaptive Behavior Composite |
| score. There are several items in each of the | , and each item is scored |
| as a The scores are summed for | each domain to generate a raw score for |
| each domain. These raw scores are also co | onverted into standard scores. The sum of |
| the standard scores for the | s the Adaptive Behavior Composite score. |
| The Vineland will be administered at V | /isit ■and ■ and will be assessed via |
| telehealth if required due to a COVID-19 re | |
| unavailable, the data will be imputed with the | e corresponding telehealth assessment. |

For each raw domain score, standardised domain score and the Adaptive Behavior Composite score, an ANCOVA will be fitted to the change from baseline to end of treatment. The model will be fitted and results presented as described in section 6.13.4.1 for the DXA scan.

Summary statistics of observed values with corresponding change from baseline will be presented as continuous by visit and treatment. Line plots will present the adjusted LS mean changes from baseline to end of treatment and SEs, as estimated by the ANCOVA, by treatment group.

The Vineland Adaptive Behavior Scale data will be listed.

6.13.4.6 Quantitative myometric measure of hand grip strength

Grip strength is recorded bilaterally, first on the right hand followed by the left hand. For each hand 3 repeat assessments are recorded. For analysis purposes, the mean of the repeat assessments is taken. Hand grip strength will be tested at Visits and and and analysis purposes.

For each hand, a MMRM will be fitted to the change from baseline over time in the mean hand grip strength (kg) in a similar manner to the primary estimand (see Section 6.13.1). Each model will include the baseline value a covariate, treatment group, age group and visit as fixed effects, and the treatment-by-visit interaction.

For each hand, the change from baseline will be summarised over time, with the observed mean at Visits and and the change from Visit to in the observed mean also summarised. The observed mean will also be presented using by subject line plots over time by treatment group separately for each hand. In addition, line plots will present the adjusted LS mean changes from baseline and SEs over time, as estimated by the MMRM model, by treatment group.

The grip strength data will be listed.

6.13.4.7 NIH Toolbox Cognition Battery

6.13.4.7.1 Dimensional Change Card Sort Test (DCCS)

The NIH Toolbox Cognition Battery: Dimensional Change Card Sort Test (DCCS) is a measure of cognitive flexibility and attention in individuals aged 3 years and older. Two target pictures are presented that vary along two dimensions (e.g., shape and color). Subjects are asked to match a series of bivalent test pictures (e.g., yellow balls and blue trucks) to the target pictures, first according to one dimension (e.g., color) and then, after a number of trials, according to the other dimension (e.g., shape). The relevant dimension for sorting is indicated by a cue word (e.g., "shape" or "color") that appears on the screen for all subjects and that, for young children ages 3-11 years, is also spoken by a pre-recorded audio file. Each administration of the test produces a raw score, computed score, uncorrected standard score, an age-corrected standard score, national percentile and full corrected T-score. The DCCS will be administered at Visit and according to the other dimensions (e.g., shape and color).

Separately for the raw score, computed score and uncorrected standard score an ANCOVA will be fitted to the change from baseline to end of treatment. The model will be fitted and results presented as described in section 6.13.4.1 for the DXA scan.

Summary statistics of observed values with corresponding change from baseline will be presented as continuous by visit and treatment. Line plots will present the adjusted LS mean changes from baseline to end of treatment and SEs, as estimated by the ANCOVA, by treatment group.

The DCCS data will be listed.

6.13.4.7.2 Picture Sequence Memory Test (PSMT)

The NIH Toolbox Cognition Battery: Picture Sequence Memory Test (PSMT) is a measure developed for the assessment of episodic memory for ages 3-85 years. It involves recalling an increasingly lengthy series of illustrated objects and activities that are presented in a particular order on the iPad screen, with corresponding audio-

recorded phrases. The sequence of pictures appears one at a time in the center of the computer screen in a fixed order. As each picture appears, a recording briefly describes its content. This continues until all pictures in a sequence have been displayed and placed in their proper positions. Once all the pictures in the sequence are displayed, the pictures then are placed in a random spatial array at the center of the screen. The subjects are asked to recall the sequence of pictures demonstrated over two learning trials; sequence length varies from 6-18 pictures, depending on age. Subjects are given credit for each adjacent pair of pictures they correctly place. The test takes approximately seven minutes to administer. Each administration of the test produces a raw score, computed score, uncorrected standard score, an age-corrected standard score, national percentile and full corrected T-score. The DCCS will be administered at Visit and

Separately for the raw score, computed score and uncorrected standard score an ANCOVA will be fitted to the change from baseline to end of treatment. The model will be fitted and results presented as described in section 6.13.4.1 for the DXA scan.

Summary statistics of observed values with corresponding change from baseline will be presented as continuous by visit and treatment. Line plots will present the adjusted LS mean changes from baseline to end of treatment and SEs, as estimated by the ANCOVA, by treatment group.

The PSMT data will be listed.

[figure not shown]
6.13.4.8 Peabody Picture Vocabulary Test (PPVT)

An ANCOVA will be fitted to the change from baseline to Week in the PPVT age-based standard score. The model will be fitted and results presented as described in section 6.13.4.1 for the DXA scan. The model will include the baseline value as a covariate and treatment group and age group as fixed effects.

The observed raw score, age-based standard score, percentile rank, age equivalent in years and months and corresponding change from baseline over time will be summarised. The above PPVT endpoints (apart from the percentile rank and age equivalent endpoints) will also be presented over time using by subject line plots by treatment group. In addition, line plots will present the adjusted LS mean changes from baseline to end of treatment and SEs, as estimated by the ANCOVA, by treatment group for the PPVT raw score and age-based standard score.

The PPVT data will be listed.

6.14 Multiplicity

For all analyses, the effects of the weight adjusted tideglusib 1000 mg dose versus placebo will be estimated at EOT and presented along with associated 95% two-sided confidence intervals and p-values. The comparisons may also be performed at other time points; however the p-values should be reviewed with caution due to potential multiplicity issue (high probability of chance-alone outcomes).

An overall false-positive rate of 5% level for the key secondary efficacy estimand will be maintained, in that no significance of key secondary estimand will be claimed unless the primary statistical analysis is significant at the 5% level.

All other secondary endpoints and the supportive analyses will be considered as supportive evidence of efficacy and will be analyzed without any procedures to account for multiple comparisons.

6.15 Concordant Trend Analysis

A supporting exploratory concordant trend analysis will be performed as described by Berry-Kravis et al., 2020; Glaze et al., 2017; Jessup et al., 2011. The approach is based on the concept that concordant trends in multiple efficacy domains may provide strong evidence of efficacy in small studies, especially when no established outcome measure exists, as for Congenital DM1. The details of this analysis are presented in the Appendix 1

The efficacy variables in this study were categorised into four different efficacy domains as shown in Table 2:

Table 2: AMO-02-MD-2-003 Outcome Variables by Efficacy Domains

The concordant trend analysis is based on a combination of group-level and subject-level analyses of the above variables. The study outcome may be indicative of overall biologic activity/efficacy if efficacy is detected for group- and/or subject-level analyses with at least a corresponding trend in the other (group- or subject-level) analyses. A corresponding trend is defined as numerical superiority of tideglusib to placebo as described for the group- and subject-level analyses but regardless of the p-values obtained for a given comparison.

The success definition is based on a combination of criteria to control the probability of a false-positive study outcome. Appendix 1 provides further details of the success criteria and analysis approach.

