As a supporting analysis, should the primary endpoint be met, the primary, key secondary and secondary endpoints may be evaluated using the permutation test (Berry-Kravis *et al.*, 2020 (accepted); Glaze *et al.*, 2017; Jessup *et al.*, 2011) based on the additional criteria for "success" specified in the SAP (for example, 3 secondary endpoints, including the key secondary, demonstrate numerical superiority of drug to placebo with the remaining secondary endpoints demonstrating non-inferiority of drug to placebo based on the prespecified threshold). Full details of the resampling procedure will be included in the Statistical Analysis Plan.

The exploratory endpoint analysis will be outlined in the SAP. The details of the analysis methods will be determined after exploratory endpoint data review.

The following exploratory endpoints, the NIH toolbox assessments (i.e. Dimensional Change Card Sort Test and Picture Sequence Memory Test) and the Peabody Picture Vocabulary Test (PPVT) will not be completed by telehealth in the event that a subject cannot attend clinic due to a COVID-19 related reason, as telehealth administration is non-standard administration for these tests. As described above, sensitivity analyses will be performed on the primary, the key secondary and one secondary endpoint to support telehealth administration, but additional sensitivity analyses for these exploratory endpoints are not planned.

A subject-level (scorecard) analysis will be performed based on the composite of primary and secondary endpoints (details will be provided in the SAP).

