6.15.1 Permutation Test

If study outcomes meet or exceed the success definition, a permutation test will be performed to determine the probability of obtaining success by chance alone. An attractive aspect of the permutation test is that it preserves the correlation structure in the study data, takes multiplicity into account and does not require additional assumptions.

If the concordant trend analysis meets the pre-specified requirements for overall efficacy specified in Appendix 1, a permutation test will be performed. The permutation test will be conducted under the assumption that there is no difference between tideglusib and placebo, thereby determining the false-positive rate on the actual study results. Randomly simulated allocations of subjects to tideglusib and placebo will be repeated 1000 times and positive outcomes will be counted. The false-positive rate for overall efficacy will be determined by:

$$False\ positive\ rate = \left(\frac{Total\ positive\ outcomes\ in\ 1000\ simulations}{1000}\right)$$

If the actual study outcomes exceeded the minimal requirements for defining overall biologic activity/efficacy as specified, then the permutation test will be performed to determine the false-positive rate based on these actual study results and not based on minimal requirements.

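### SAP 6.15 and 6.15.1 omit the protocol's condition that the primary endpoint be met before the permutation-tested success analysis is used, and SAP 6.18 does not declare it

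*SAP*

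**What the plan says.** **Protocol 11.5** sets the condition: "As a supporting analysis, should the primary endpoint be met, the primary, key secondary and secondary endpoints may be evaluated using the permutation test". It leaves the success criteria to the SAP and gives an example based on numerical superiority on some secondary endpoints and non-inferiority on the rest. Further on, without any condition, it adds: "A subject-level (scorecard) analysis will be performed based on the composite of primary" and secondary endpoints.

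**SAP 6.15** opens with: "A supporting exploratory concordant trend analysis will be performed". The primary result is not mentioned as a precondition. The criterion for a positive reading is: "The study outcome may be indicative of overall biologic activity/efficacy if efficacy is detected for group- and/or subject-level analyses", with at least a corresponding trend at the other level. A trend means numerical superiority of tideglusib, "regardless of the p-values obtained for a given comparison".

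**SAP 6.15.1** gives the trigger for the permutation test: "If the concordant trend analysis meets the pre-specified requirements for overall efficacy specified in Appendix 1, a permutation test will be performed". Treatment labels are reshuffled 1000 times, and the share of positive outcomes is reported as the false-positive rate. The visible text gives no cut-off for that rate.

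**SAP 6.14** makes a key secondary claim depend on a significant primary at the 5% level. Everything else is supportive and unadjusted.

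**SAP 6.18** lists three changes from the protocol: the added Enrolled and Run-in sets, the revised ITT definition, and the evaluation of CDM1-RS measurement properties.

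**The concern.** The protocol's condition decides what may be said after a failed primary. With it, the success analysis can only reinforce a positive primary result. Without it, the analysis can yield a positive study-level statement on its own, with a number that works much like a p-value. SAP 6.15 also says that concordant trends may be strong evidence in small studies. With 53 children randomized (SAP section 3), a missed primary is a realistic case, and it is the case that the protocol's condition governs. If the two documents are not reconciled, the study report can follow either rule.

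**Working it through.** **Step 1. Is it the same analysis?** Protocol 11.5 and SAP 6.15 support the method with the same three cited trials: two trofinetide trials and a cardiac gene-therapy trial. Both describe success criteria checked by permutation. SAP 6.15.1 is therefore the detailed form of what Protocol 11.5 permits.

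**Step 2. The two texts side by side.**

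| Element | Protocol 11.5 | SAP 6.15 / 6.15.1 (visible text) |
|---|---|---|
| Status | Supporting, optional | Supporting and exploratory, always run |
| Precondition for the permutation test | Primary endpoint met | Own success definition met |
| Subject-level scorecard | Unconditional | One of the two levels combined |
| Success criteria | Deferred to the SAP | Summarised; details in Appendix 1 (not visible) |

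**Step 3. Can a failed primary coexist with a positive reading?** The criterion accepts efficacy at group level, at subject level, or both. The level without a finding needs only numerical superiority. A subject-level finding plus a non-significant group-level advantage therefore satisfies the visible text, so a non-significant primary does not block the statement.

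**Step 4. Is the change declared?** None of the three items in SAP 6.18 concerns it. The SAP introduction cites protocol version 8.0, whereas the protocol reviewed is version 9.0 of 02 February 2023. The SAP is dated 22 February 2023, so it could have been aligned with the current protocol.

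**Step 5. The plan's own figure.** SAP 6.14 states an overall 5% false-positive rate for the primary followed by the key secondary. A simulation of that sequence with 2 million null draws gives 5.03%, 5.00% and 5.02% at correlations 0, 0.5 and 0.9. The stated 5% is reproduced.

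**Step 6. Illustration of an unconditional second route.** Count only results favouring tideglusib under the null. Let a1 = 0.025 be the primary's chance and a2 the assumed chance that the success analysis is accepted, with bivariate-normal correlation rho:

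P(either) = a1 + a2 − P(Z1 > z1, Z2 > z2)

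At rho = 0 and a2 = 0.025: 0.025 + 0.025 − 0.025 × 0.025 = 0.0494.

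| Assumed a2 | rho 0 | rho 0.5 | rho 0.7 | rho 0.9 |
|---|---|---|---|---|
| 0.025 | 4.9% | 4.5% | 4.2% | 3.5% |
| 0.05 | 7.4% | 6.8% | 6.3% | 5.5% |

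If the primary is counted in both directions and a2 = 0.05, the range is 9.75% (rho 0) to 8.0% (rho 0.9).

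With the protocol's condition, a success statement can occur only inside a positive primary. P(either) is then P(primary): 2.5% in the favourable direction, or 5% counted both ways.

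**The case against.** The strongest reply is that this is labelled exploratory and should be read that way. SAP 6.15 calls it supporting and exploratory and says only that the outcome may be indicative. SAP 6.14 reserves formal claims for the primary and key secondary, and that hierarchy is intact. This stands. A reader might infer that the trial has two confirmatory chances and that its 5% error rate is broken, but the documents do not support that. The second route leads to a supportive statement, and the figures in Step 6 are not an error rate of the plan.

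Four further points on the other side:

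- **Appendix 1 is not visible.** It could contain a primary-endpoint requirement, so it cannot be shown that the permutation test would run after a failed primary. Such a requirement would fit poorly with the criterion in 6.15, which accepts a finding at either level. The point is therefore confined to the visible text.
- **The protocol does not gate everything.** It conditions the permutation test on the success criteria, not the scorecard. Its own example uses numerical superiority, so the SAP's trend criterion is not a relaxation in itself.
- **Scope.** A reader might infer that the SAP also widened the endpoint list, because it spans four efficacy domains and the protocol's readable biomarker/physiological endpoints are exploratory. The contents of Table 2 are not shown, and the four domains come from Protocol 10.1. This cannot be verified and is not part of the point.
- **Version.** Section 6.18 may have been written against protocol 8.0, which is not available. That could explain the omission, but the SAP would still need to be aligned with version 9.0.

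**Conclusion.** The inconsistency holds on the visible text. Protocol 11.5 conditions the permutation-tested success analysis on the primary endpoint, SAP 6.15 and 6.15.1 do not, and SAP 6.18 does not say so. The consequence is that a supportive statement of overall biologic activity or efficacy, with a permutation rate attached, remains open after a non-significant primary. The primary test and the key secondary gate are unaffected.

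The size cannot be derived from the documents, which give neither a cut-off for the permutation rate nor a correlation with the primary. The rise from 2.5% to about 4% to 7% rests on assumed cut-offs of 2.5% or 5% and correlations of 0.5 to 0.7, and it shrinks as the correlation approaches 1. The direction holds unless the analysis can succeed only when the primary does. This is a consistency and interpretation point that should be fixed. It is not a defect in the confirmatory analysis.

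**What to change.** In SAP 6.15 and 6.15.1, state that the permutation test and any interpretation as overall efficacy apply only if the primary MMRM is significant at the two-sided 5% level in favour of tideglusib. Otherwise, report the concordant trend results descriptively, with no efficacy conclusion. The scorecard summary in Protocol 11.5 can still be produced, since the protocol does not condition it. List any remaining departure from Protocol 11.5 in SAP 6.18 with its reason, and check that Appendix 1 says the same.

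The SAP addendum of 22 August 2024 already describes post-hoc analyses. If the data are unblinded, the study report should apply the protocol's condition and disclose the discrepancy.

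The cost is wording only. The downside is that the composite cannot serve as positive evidence after a failed primary.

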6.15.1 Permutation Test

If study outcomes meet or exceed the success definition, a permutation test will be performed to determine the probability of obtaining success by chance alone. An attractive aspect of the permutation test is that it preserves the correlation structure in the study data, takes multiplicity into account and does not require additional assumptions.

If the concordant trend analysis meets the pre-specified requirements for overall efficacy specified in Appendix 1, a permutation test will be performed. The permutation test will be conducted under the assumption that there is no difference between tideglusib and placebo, thereby determining the false-positive rate on the actual study results. Randomly simulated allocations of subjects to tideglusib and placebo will be repeated 1000 times and positive outcomes will be counted. The false-positive rate for overall efficacy will be determined by:

$$False\ positive\ rate = \left(\frac{Total\ positive\ outcomes\ in\ 1000\ simulations}{1000}\right)$$

If the actual study outcomes exceeded the minimal requirements for defining overall biologic activity/efficacy as specified, then the permutation test will be performed to determine the false-positive rate based on these actual study results and not based on minimal requirements.

